7.1.1 Molecular pre-screening

Not applicable.

7.1.2 Screening

Written informed consent/assent must be obtained prior to any screening procedures. Screening assessments to confirm eligibility into the study should be performed as per visit evaluation schedule between Day-28 and Day-1. Serum pregnancy test must be conducted within 72 hours prior to start of study treatment and must be confirmed negative before the first dose of study treatment. Physical examinations and laboratory assessments performed as part of the screening evaluations will not require to be repeated prior to dosing if performed within 7 days prior to the first dose of study treatment. Laboratory results from the central laboratory will be used to determine subject's eligibility. However, the site does not need to wait for the results of centrally-analyzed laboratory assessments when an immediate clinical decision needs to be made and in those cases locally unscheduled testing may be performed and used for eligibility assessments.

The cardiac eligibility criteria should be assessed with the local ECG report.

A subject who has a laboratory test result(s) that does not satisfy the entrance criteria may have the test(s) repeated. These test(s) may be repeated as soon as the investigator believes the re-test result(s) is/are likely to be within the acceptable range to satisfy the entrance criteria, but should be completed within approximately 3 weeks of the original screening visit date. In this case, the subject will not be required to sign another ICF, and the original subject ID number assigned by the investigator will be used. In the event that the laboratory test(s) cannot be performed within 3 weeks of the original screening visit, or the re-test(s) do not meet the entrance criteria, or other eligibility criteria have changed and are not met anymore, the subject is considered a screen failure.

A new ICF will need to be signed if the investigator chooses to re-screen the subject after a subject has screen failed, however, the subject ID number will remain the same. All required screening activities must be performed when the subject is re-screened for participation in the study. An individual subject may only be re-screened once for the study. Once the number of subjects screened and enrolled is likely to ensure target enrollment, the Sponsor may close the study to further screening. In this case, the subjects who screen failed will not be permitted to re-screen.

Subjects will be enrolled based on local *BRAF* V600 mutation result as part of study inclusion criteria 9 (applicable to all study cohorts). The *BRAF* V600 mutation will be assessed using a validated tissue-based molecular test for *BRAF* V600 mutations. Immunohistochemistry is not an accepted method and liquid biopsy based *BRAF* V600 results cannot be used to enroll patients. The eCRF page for methods of local BRAF mutation testing must be completed for subjects whose tumor sample was tested by a local institutional assay. Verification of locally documented *BRAF* V600 mutation result must be completed prior to randomization. If the local lab uses a non-FDA approved BRAF V600 assay (FDA approved tests for BRAF V600 mutations include: biomerieux THxID® BRAF Detection Kit and Roche Cobas 4800 BRAF

V600 Mutation Test), information about the assay must be provided to the Sponsor or representative for review.

BRAF V600 mutation results will be subjected to retrospective central confirmation by a Novartis designated laboratory and FDA approved assay (e.g., Biomerieux THxID™-*BRAF*).

For the retrospective central confirmation all subjects will be required to provide a tumor tissue sample at screening prior to study treatment, as either a tumor block or a minimum of 25 FFPE slides (see [Section 7.2.4](#)). Central confirmation of *BRAF* V600 mutation status is not required for enrollment if other inclusion and exclusion criteria are fulfilled. Subjects will not be excluded if centralized testing is later found to be discordant or uninformative (e.g., inadequate sample).

For subjects who do not have a *BRAF* V600 mutation result documented locally, **a tumor sample (tumor block or minimum 25 slides)** must be submitted for central testing of *BRAF* mutation status by day -20. The test to confirm *BRAF* V600 activating mutation will be performed either using archival tissue, or preferably, using a new biopsy prior to study entry.

 Please see [Table 7-12](#) and [Table 7-13](#) for details on the tumor sample requirement for central *BRAF* V600 mutation testing and additional biomarker studies.

7.1.2.1 Eligibility screening

Following registering in the IRT for screening, subject eligibility will be checked once all screening procedures are completed. The eligibility check will be embedded in the IRT system. Please refer and comply with detailed guidelines in the IRT manual.

7.1.2.2 Information to be collected on screening failures

Subject who signed an Informed Consent Form but failed to be started on treatment for any reason will be considered a screen failure. Subjects who are found not eligible after signing the main study consent will be considered as screening failures, and data will be handled in the same manner.

The following eCRFs should be completed for screen failures:

- Study part
- Demography
- Informed Consent
- Screening Phase Disposition
- Inclusion/Exclusion Criteria
- Biomarker Assessment - *BRAF* V600 Mutation Local Result

No other data will be entered into the clinical database for subjects who are screen failures, unless the subject experienced a Serious Adverse Event during the Screening Phase (see [Section 8](#) for SAE reporting details).

7.1.2.3 Subject demographics and other baseline characteristics

The data to be collected on subject characteristics at screening includes:

- Demography (age, gender, childbearing potential, race and ethnicity, or as allowed by local regulations)
- Past and current medical conditions including cardiovascular medical history and risk factors
- Diagnosis and extent of cancer using AJCC edition 7 and 8
- Alcohol history
- Smoking history
- HIV history (for Germany only: HIV test is required during screening using a local test)
- Prior antineoplastic therapies (medications, radiation, surgeries)
- Prior and current concomitant medications, surgical and medical procedures and significant non-drug therapies

[figure not shown]
Note: All other medications taken within 28 days or 5 half-lives, whichever is shorter before the first dose of study treatment is administered must be recorded on the Prior and current concomitant medication eCRF page and updated on an ongoing basis if there is new change to the medication.

Assessments to be performed at screening/baseline include;

- Physical examination (e.g., performance status (ECOG), height, weight, vital signs, ophthalmic and skin examination)
- Cardiovascular assessments (e.g., ECG, ECHO or MUGA)
- Laboratory assessments (e.g., hematology, chemistry, thyroid function, coagulation, urinalysis, serum pregnancy test, hepatitis B, C test, and [REDACTED])
- Tumor assessment (RECIST 1.1, color digital photography (including metric ruler for skin lesions))
- Biomarker assessments in [REDACTED] tumor tissue

7.1.3 Treatment period

- Study treatment will begin on Day 1 of Cycle 1.
- Study treatment will continue until the subject experiences any of the following: disease progression according to RECIST 1.1 as determined by investigator, unacceptable toxicity that precludes further treatment, pregnancy, start of a new anti-cancer therapy, discontinuation at the discretion of the Investigator or subject, lost to follow-up, death, or study termination by the sponsor.
- Subjects may continue study treatment beyond disease progression by RECIST 1.1 until disease progression per response criteria for immunotherapy (if criteria stipulated in [Section 6.1.5.1](#) are fulfilled), unacceptable toxicity, start of new anti-neoplastic therapy, withdrawal of consent, physician's decision, lost to follow-up, death, or study is terminated by the sponsor. In case of continuation of study treatment beyond disease progression by RECIST 1.1, the subject will continue tumor assessments as outlined in [Section 7](#).

Visit frequency

- Safety run-in part: visits will be scheduled for C1D1, (C1D8 for DL1 and DL-1a only), C1D15, C2D1, (C2D8 for DL-1b only), C2D15, C3D1, C3D15, C4D1, (C4D15 for DL-1a only), C5D1, and every 4 weeks thereafter. For details of assessment, refer to [Table 7-1](#).
- Biomarker cohort: visits will be scheduled for C1D1, C1D15, C2D1, C2D15, C3D1, C3D15, C4D1, and every 4 weeks thereafter. For details of assessment, refer to [Table 7-2](#).
- Randomized part: visits will be scheduled for C1D1, C1D15, C2D1, C2D15, C3D1, and every 4 weeks thereafter. For details of assessment, refer to [Table 7-3](#).

Windows for scheduling assessments

- Every effort must be made to follow the schedule of assessments within the windows outline in the protocol.
- For Cycle 1, all assessments have a ± 3 day window, unless otherwise indicated.
- After Cycle 1, all assessments have a ± 7 day window, unless otherwise indicated.
- Subjects who discontinue study treatment must have an End of Treatment (EOT) visit performed ≤ 7 days after stopping study treatment.

7.1.4 Discontinuation of study treatment

Subjects may voluntarily discontinue from the study treatment for any reason at any time. If a subject decides to discontinue from the study treatment, the investigator should make a reasonable effort (e.g., telephone, e-mail, letter) to understand the primary reason for this decision and record this information in the subject's chart and on the appropriate eCRF pages. They may be considered withdrawn if they state an intention to withdraw, fail to return for visits, or become lost to follow-up for any other reason.

The investigator may discontinue study treatment for a given subject if, he/she believes that continuation would be detrimental to the subject's well-being.

Study treatment must be discontinued under the following circumstances:

- Emergence of specific adverse events or laboratory abnormalities under some circumstances as outlined in [Section 6.3](#).
- Pregnancy (pregnancy will be followed for outcome)
- Use of prohibited treatment
- Any protocol deviation that results in a significant risk to the subject's safety

Subjects who become pregnant during the trial must be withdrawn ([Section 8.4](#)). Subjects who become pregnant must cease all tumor assessments regardless of whether or not they developed Progressive Disease according to investigator.

Subjects who discontinue study treatment should NOT be considered withdrawn from the study. They should return for the assessments indicated in [Section 7.2](#). If they fail to return for these assessments for unknown reasons, every effort (e.g., telephone, email, and letter) should be made to contact them as specified in [Section 7.1.9](#).

Subjects who discontinue study treatment should be scheduled for an EOT visit as soon as possible and within 7 days of the last dose of study treatment, at which time all of the

assessments listed for the EOT visit will be performed. If a subject is discontinued from treatment at a study visit, the assessments performed at that visit will be considered as EOT assessments and do not need to be repeated. An End of Treatment Disposition eCRF page should be completed, giving the date and reason for stopping treatment. Subjects who discontinue due to disease progression should have an EOT visit and have disease progression biomarker samples collected.

The investigator must also contact the IRT to register the subject's discontinuation from study treatment.

In some circumstances subjects may be allowed to continue to receive study treatment beyond disease progression as per RECIST 1.1 criteria ([Section 6.1.4](#)). These subjects will continue assessments as outlined in [Section 7](#), and will complete the EOT visit only after permanent discontinuation of study treatment.

The physician can decide to discontinue the study treatment based on the risk benefit assessment following a discussion with the patient.

Following final PFS analysis and results, subjects who discontinue treatment, for any reason, must continue to be followed for safety assessments and as part of the overall survival follow-up until death, lost to follow-up, or withdrawal of consent as described in [Section 7](#).

Patients who have accepted to move to Post-Trial Access (PTA), as per local regulation, will perform the end of treatment visit. Upon completion of this visit, no further safety and survival follow-up will be conducted under this protocol for these patients.

7.1.4.1 Replacement policy

Part 1: Safety run-in

If a subject is considered as non-evaluable for the Dose-Determining Set (DDS), a new subject will be enrolled until at least the minimum number of 6 evaluable subjects is achieved within the cohort.

Part 2: Biomarker cohort

If not possible to collect at least three tumor biopsies (at screening, C1D15 and one additional biopsy on treatment), a new subject will be enrolled to allow for a sufficient number of evaluable subjects for the biomarker studies.

Part 3: Double-blind, randomized, placebo-controlled part

Subjects will not be replaced.

7.1.5 Withdrawal of study consent

Subjects may voluntarily withdraw consent to participate in the study for any reason at any time. Withdrawal of consent occurs only when a subject does not want to participate in the study any longer, and does not allow any further collection of personal data.

If a subject withdraws consent, the investigator should make a reasonable effort (e.g., telephone, e-mail, letter) to understand the primary reason for the subject's decision to withdraw his/her consent and record this information.

Study treatment must be discontinued and no further assessments conducted, and the data that would have been collected at subsequent visits will be considered missing.

Further attempts to contact the subject are not allowed unless safety findings require communication or follow up.

All efforts should be made to complete the assessments prior to study withdrawal. A final evaluation at the time of the subject's study withdrawal should be made as detailed in the assessment table.

Novartis will continue to keep and use collected study information (including any data resulting from the analysis of a subject's samples until their time of withdrawal) according to applicable law.

For US and Japan: All biological samples not yet analyzed at the time of withdrawal may still be used for further testing/analysis in accordance with the terms of this protocol and of the informed consent form.

For EU and Rest of World (RoW): All biological samples not yet analyzed at the time of withdrawal will no longer be used, unless permitted by applicable law. They will be stored according to applicable legal requirements.

7.1.6 Follow up for safety evaluations

All subjects must be followed for safety up to 150 days after the last dose of PDR001/placebo. After the 30-day onsite safety follow-up visit, subjects will be followed (via telephone call or onsite visit if subject happens to be visiting the site) at 60, 90, 120 and 150 days after the last dose of PDR001/placebo ([Appendix 3](#)).

In case where individual drug components of the study treatment are discontinued at different times, subjects must be followed for safety evaluation up to 150 days following the last dose of PDR001/placebo or up to 30 days after the last dose of dabrafenib or 120 days after the last dose of trametinib, whichever is longer. In addition, subjects will be followed for skin related toxicity every month for 6 months from the last dose of dabrafenib.

All safety assessments should be completed outlined in [Section 7.1](#). However, if the subject begins post treatment antineoplastic medication before the 150-Day safety follow-up visit the collection of new SAEs and AEs unrelated to study medication will stop and thereafter only suspected AEs and suspected SAEs will continue to be collected up to Day 150. Suspected SAEs will continue to be collected beyond the 150-Day safety visit. Data collected should be added to the appropriate eCRF pages. For female subjects of child bearing potential, a pregnancy test will be performed at the time points listed in [Section 7.1](#).

Data collected should be added to the Adverse Events eCRF and the Concomitant Medications eCRF.

Following the final PFS analysis and results, safety assessments will continue per protocol schedules outlined in [Table 7-1](#), [Table 7-2](#) and [Table 7-3](#).

For subjects who transferred to Post-Trial Access (PTA), no further safety follow-ups will be performed.

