[Part 2 of 2 of the document. The other parts are not shown.]

[figure not shown]
	Category	Protocol Section	Screening/ Baseline	Treatment (Cycle = 28 days)									Follow-Up Period									
				Cycle 1			Cycle 2			Cycle 3			Subsequent Cycles Day 1	End of Study Treatment (EoT)	30- Day Safety Follow Up	60-Day Safety Follow Up	90-Day Safety Follow Up	120-Day Safety Follow Up	150 Day Safety Follow Up	End of Post Treatment Follow Up	Survival Follow Up	
Day of cycle			-28 to -1	1	8	15	1	8	15	1	15	1										
Enrollment																						
Drug Supply (IRT)	S	7.1.2.1	X																			
Disposition Assessment (at the end of each study phase)	D	7.1.4	X											X							X	
Physical Examination																						
Physical Examination (complete)	S	7.2.2.1	X	As clinically indicated																		
Physical Examination (short)	S	7.2.2.1		X			X			X		X		X		30 days from the last dose of PDR001 and every month for 6 months from the last dose of dabrafenib						
Performance Status (ECOG)	D	7.2.2.4	X	X			X			X		X		X	X							
Height	D	7.2.2.3	X																			
Weight	D	7.2.2.3	X	X			X			X		X		X	X							
Vital signs	D	7.2.2.2	X	X			X			X		X		X	X							

[figure not shown]
	Category	Protocol Section	Screening/Baseline	Treatment (Cycle = 28 days)										Follow-Up Period						
				Cycle 1			Cycle 2			Cycle 3		Subsequent Cycles Day 1	End of Study Treatment (EoT)	30- Day Safety Follow Up	60-Day Safety Follow Up	90-Day Safety Follow Up	120-Day Safety Follow Up	150 Day Safety Follow Up	End of Post Treatment Follow Up	Survival Follow Up
				1	8	15	1	8	15	1	15									
Day of cycle			-28 to -1	1	8	15	1	8	15	1	15	1								
Ophthalmic examination	D	7.2.2.5	X				X			As clinically indicated										
12-lead ECG for DL1	D	7.2.2.7.1	X				X			As clinically indicated		X								
12-lead ECG for DL-1a or DL-1b	D	7.2.2.7.1	X							X		As clinically indicated	X							
Cardiac function (MUGA or ECHO)	D	7.2.2.7.2	X				X					C4D1 and every 12 weeks and as clinically indicated	X							
Laboratory Assessments																				
Hematology for DL1	D	7.2.2.6.1	X	X	X	X	X		X	X	X	X	X	X						
Hematology for DL-1a	D	7.2.2.6.1	X	X	X	X	X		X	X	X	X and at C4D15	X	X						
Hematology for DL-1b	D	7.2.2.6.1	X	X		X	X	X	X	X	X	X	X	X						
Chemistry for DL1	D	7.2.2.6.1	X	X	X	X	X		X	X	X	X	X	X						
Chemistry for DL-1a	D	7.2.2.6.1	X	X	X	X	X		X	X	X	X and at C4D15	X	X						
Chemistry for DL-1b	D	7.2.2.6.1	X	X		X	X	X	X	X	X	X	X	X						

[figure not shown]

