PRO questionnaires should be administered at beginning of the scheduled study visit, prior to any tests performed, treatments administered or receipt of test results.																
EORTC QLQ-C30	D	7.2.5.1	X						Following final PFS analysis; PRO assessments will no longer be collected.							
EQ-5D-5L	D	7.2.5.2	X						Following final PFS analysis; PRO assessments will no longer be collected.							
FACT-M subscale (16 questions)	D	7.2.5.3	X						Following final PFS analysis; PRO assessments will no longer be collected.							

[figure not shown]

	Category	Protocol Section	Screening/Baseline	Treatment (Cycle = 28 days)						Follow-Up Period								
				Cycle 1		Cycle 2		Subsequent cycles Day 1	End of Study Treatment (EoT)	30 Day Safety Follow Up	60- Day Safety Follow Up	90- Day Safety Follow Up	120- Day Safety Follow Up	150- Day Safety Follow Up	End of Post Treatment Follow Up	Survival Follow Up		
Day of cycle			-28 to -1	1	15	1	15										1	1
Physical Examination																		
Physical Examination (complete)	S	7.2.2.1	X	As clinically indicated														
Physical Examination (short)	S	7.2.2.1		X		X		X	X	30 days from the last dose of PDR001/placebo and every month for 6 months from the last dose of dabrafenib								
Performance Status (ECOG)	D	7.2.2.4	X	X		X		X	X	X								
Height	D	7.2.2.3	X															
Weight	D	7.2.2.3	X	X		X		X	X	X								
Vital signs	D	7.2.2.2	X	X		X		X	X	X								
Ophthalmic examination	D	7.2.2.5	X			X		As clinically indicated										
12-lead ECG if DL1 is determined to be the regimen	D	7.2.2.7.1	X			X		As clinically indicated	X									
12-lead ECG if DL-1a or DL-1b is determined to be the regimen	D	7.2.2.7.1	X					C3D1, and as clinically indicated	X									

[figure not shown]

	Category	Protocol Section	Screening/Baseline	Treatment (Cycle = 28 days)						Follow-Up Period							
				Cycle 1		Cycle 2		Subsequent cycles Day 1	End of Study Treatment (EoT)	30 Day Safety Follow Up	60- Day Safety Follow Up	90- Day Safety Follow Up	120- Day Safety Follow Up	150- Day Safety Follow Up	End of Post Treatment Follow Up	Survival Follow Up	
Day of cycle			-28 to -1	1	15	1	15										1
Cardiac function (MUGA or ECHO)	D	7.2.2.7.2	X			X		C4D1 and every 12 weeks and as clinically indicated	X								
Laboratory Assessments																	
Hematology	D	7.2.2.6.1	X	X	X	X	X	X	X								
Chemistry	D	7.2.2.6.2	X	X	X	X	X	X	X								
Thyroid function-TSH	D	7.2.2.6.3	X	X		X		X	X								

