Chemistry	Albumin, Alkaline phosphatase, ALT, AST, Lactate dehydrogenase (LDH), Calcium, Magnesium, Phosphorus, Sodium, Potassium, Chloride, Creatinine, Creatine kinase, Direct Bilirubin, Total Bilirubin, Total Cholesterol, Blood Urea Nitrogen (BUN) or Urea, Uric Acid, Amylase, Lipase, Glucose (fasting or non-fasting)
Thyroid	At baseline: TSH (Thyroid Stimulation Hormone), Free T3 and Free T4 At the subsequent visits as indicated in Table 7-1 , Table 7-2 and Table 7-3 : TSH only. If TSH is abnormal, central lab will test Free T3 and Free T4
Coagulation	International normalized ratio (INR), Activated partial thromboplastin time (APTT)
Urinalysis	Local Laboratory: Macroscopic Panel (Dipstick) (Color, Bilirubin, Blood, Glucose, Ketones, Leukocytes esterase, Nitrite, pH, Protein, Specific Gravity, Urobilinogen) If dipstick is abnormal then perform local laboratory Microscopic Panel (Red Blood Cells, White Blood Cells, Casts, Crystals, Bacteria, Epithelial cells)
Pregnancy Test	A serum pregnancy test must be performed at screening (at the local laboratory) \leq 72 hours before first dose of study treatment, at EOT, at 30-day and 150 day safety follow-up. A local laboratory urine pregnancy test must be performed at day 1 of every cycle beginning with cycle 2, and at home every 30-days after the 30-day safety follow-up visit until 120-day follow-up.
Hepatitis markers	HBV-DNA, HbsAg, HbsAb, HbcAb, HCV RNA-PCR
Virology	For Germany only: Local HIV testing at screening

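### When trametinib outlasts PDR001/placebo by more than 150 days, follow-up visits dated from PDR001/placebo leave no scheduled pregnancy test after the end-of-treatment test

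*Protocol*

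**What the plan says.** **Visit dates.** Section 7.1.6 places the contacts after the 30-day visit "at 60, 90, 120 and 150 days after the last dose of PDR001/placebo". The short physical examination row of Table 7-3 reads "30 days from the last dose of PDR001/placebo and every month for 6 months from the last dose of dabrafenib". Tables 7-1 and 7-2 have the same row without placebo: "30 days from the last dose of PDR001 and every month for 6 months from the last dose of dabrafenib". Footnote c of Table 7-8 and footnote b of Table 7-9 deal expressly with PDR001 (or placebo) being stopped for good ahead of the oral drugs. They keep the 30- and 150-day safety visits counted from PDR001/placebo.

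**Length of follow-up.** For components stopped at different times, 7.1.6 runs safety evaluation to 150 days after PDR001/placebo "or up to 30 days after the last dose of dabrafenib or 120 days after the last dose of trametinib, whichever is longer". Sections 8.1.1 and 8.2.2 apply the dabrafenib/trametinib extension only if the partner drug went on for more than 150 days after PDR001/placebo.

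**Pregnancy tests.** Section 7.1.6 handles these separately: "For female subjects of child bearing potential, a pregnancy test will be performed at the time points listed in" Section 7.1. Section 7.2.2.6.6 and Table 7-6 give Day 1 urine tests from Cycle 2, then serum tests at EOT and at the 30- and 150-day visits. Home urine tests fall between, "and at home every 30-days after the 30-day safety follow-up visit until 120-day follow-up". Tables 7-1 to 7-3 show all these visits in columns after EoT.

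**Current status.** "Following the final PFS analysis and results, safety assessments will continue per protocol schedules outlined in" Tables 7-1 to 7-3. Section 8.3 stops placebo in the placebo arm. Patients who move to Post-Trial Access leave the schedule: "For subjects who transferred to Post-Trial Access (PTA), no further safety follow-ups will be performed".

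**The concern.** The protocol sets a safety period counted from trametinib but leaves the visits inside that period counted from another drug. If all drugs stop together, a woman of child-bearing potential has five scheduled pregnancy tests after EOT. If she stays on dabrafenib/trametinib for more than 150 days after PDR001/placebo, she has none, although 7.1.6 follows her for 120 days after trametinib.

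The situation is foreseeable. Placebo-arm women still on dabrafenib/trametinib under this protocol meet it once placebo is stopped under 8.3. The same anchor puts the 30-day on-site visit before the last active dose whenever the lag exceeds 30 days. What is at stake is the timely detection of a pregnancy after the oral drugs end. No efficacy endpoint or error rate is involved.

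**Working it through.** The plan states no figure to reproduce, so this is date arithmetic.

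**Inputs**
- Day 0 is the last PDR001/placebo dose and day G the last trametinib dose. Dabrafenib is assumed to stop on day G too.
- Visit-based tests fall on days 30, 60, 90, 120 and 150 (7.1.6, 7.2.2.6.6, Table 7-6).
- The EOT test falls within 7 days of the last dose, on days G to G+7 (7.1.4).
- Follow-up under 7.1.6 ends on day max(150, G+30, G+120) = max(150, G+120).

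**Formulae**
- G+120 exceeds 150 exactly when G > 30.
- The last visit-based test falls 150−G days after trametinib. Shortfall = max(0, 120−(150−G)) = max(0, G−30).
- From G = 144 the EOT test may be later than the 150-day visit. For G of 150 or more it is the last test, or falls with it, and the shortfall is 120−7 to 120−0 = 113 to 120 days.
- Further tests needed = min(4, (G−30)/30 rounded up), and 0 if G is 30 or less.
- The 30-day visit falls 30−G days relative to the last trametinib dose.

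**Results** (nominal dates)

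| G | Follow-up ends (day) | Visit-based tests, days after trametinib | Shortfall (days) | Further tests |
|---|---|---|---|---|
| 28 | 150 | 2, 32, 62, 92, 122 | 0 | 0 |
| 31 | 151 | 29, 59, 89, 119 | 1 | 1 |
| 56 | 176 | 4, 34, 64, 94 | 26 | 1 |
| 84 | 204 | 6, 36, 66 | 54 | 2 |
| 112 | 232 | 8, 38 | 82 | 3 |
| 140 | 260 | 10 | 110 | 4 |
| 168 | 288 | none | 113–120 | 4 |

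At G = 56, 84 and 112 the 30-day visit falls 26, 54 and 82 days before the last trametinib dose. A joint stop within one 4-week PDR001 interval gives G of at most 28 and no shortfall.

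**Which rule applies**
- For G above 150, both 7.1.6 and 8.1.1/8.2.2 extend follow-up to 120 days after trametinib. The shortfall of at least 113 days holds under either.
- For G of 31 to 150, only the 7.1.6 wording gives the longer window. At G = 120, for example, 7.1.6 runs to day 240, while the trametinib extension in 8.1.1 and 8.2.2 is not triggered.
- For G of 31 to 37 the shortfall is 1 to 7 days, inside the ±7-day window of 7.1.3.

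**The case against.** The strongest counter-argument is that the protocol orders these visits after EOT. Tables 7-1 to 7-3 place the columns there, and 7.2.2.6.6 reads as a sequence from treatment to EOT to follow-up without naming PDR001 as the anchor. A site could sensibly count from the last dose of any drug. The footnotes belong to PK/IG tables whose sampling ended with the 01-Jul-2020 cut-off, and the short-examination row does not govern pregnancy tests. The Appendix 3 flow chart, which 7.1.6 cites, is not visible and might settle the matter. The first part of the protocol is not at hand either.

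Much of this stands as a limit on the point, but it does not remove it. The 7.1.6 sentence names PDR001/placebo explicitly. The footnotes speak of the safety visits themselves, in exactly the situation at issue. Column order does not supply a date. At best the text pulls two ways, and a site that follows the explicit wording leaves the gap.

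A reader might infer that the protocol breaks its own requirement. It does not: the 120 days are for safety evaluation, and no visible text requires pregnancy tests throughout them. A reader might also infer that every lag above 30 days leaves a gap under every section. The separate trigger in 8.1.1 and 8.2.2 rules that out. Nor are these women unmonitored. Day 1 urine tests on treatment, the EOT test, AE/SAE collection and monthly examinations after dabrafenib remain. Women are also told to contact the site at once after a positive test, although that presupposes that a test is done.

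**Conclusion.** The point holds as a low-cost safety improvement. The firm case is a lag above 150 days: no scheduled pregnancy test follows the EOT test, and at least 113 of the 120 days of post-trametinib follow-up have none, whichever section is applied. For lags of 31 to 150 days the shortfall is up to G−30 days under 7.1.6 only, and up to 7 days of it is within visit tolerance. For lags of 30 days or less there is none.

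This rests on nominal visit dates, on dabrafenib and trametinib stopping together, and on Appendix 3 not re-dating the visits. If dabrafenib continued after trametinib, on-treatment urine tests would cover part of the window. The document does not give the number of women affected, and those moving to Post-Trial Access are outside the issue.

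**What to change.** For subjects who stay under the protocol and do not move to Post-Trial Access:

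- In 7.1.6, 7.2.2.6.6, Table 7-6 and Tables 7-1 to 7-3 (including the short-examination row), date the 30-day visit from the last dose of any study drug. Section 10.5.3.1 already counts the on-treatment period that way.
- Continue post-EOT pregnancy tests every 30 days, as home urine tests where possible, to the later of 150 days after PDR001/placebo and 120 days after trametinib.
- Limit the footnotes of Tables 7-8 and 7-9 to PK/IG sampling.
- Align the extension trigger in 8.1.1 and 8.2.2 with 7.1.6, and Appendix 3 if needed.

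The cost is amendment wording, one re-dated on-site visit per affected subject, and at most four further simple tests per affected woman. While she stays on dabrafenib/trametinib, the Day 1 visits every 4 weeks already cover the first 30 days after PDR001/placebo. Aligning 8.1.1 and 8.2.2 also lengthens AE/SAE collection for lags of 31 to 150 days.
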